3.2. SCHEDULE OF EVENTS

Schedule of events can be found in Sections “FLOW CHART A: SCREENING AND INDUCTION PERIOD” and “FLOW CHART B: MAINTENANCE PERIOD” of the protocol.

Document: \\ieedc-
vnasc01\BIOSdata\Boehringer_Ingelheim\BI_695501\NVA96252\Biostatistics\Documentation\SAP\BI1297.4 SAP FINAL v4.0_22MAY2019.docx

Author: Version Number: Final V4.0
Version Date: 22MAY2019

Template No: CS_TP_BS016 Revision 5 Reference: CS_WI_BS005
Effective Date: 01Apr2018

Copyright © 2009, 2010, 2012, 2016, 2018 All rights reserved. The contents of this document are confidential and proprietary to Holdings Inc. and its subsidiaries. Unauthorized use, disclosure or reproduction is strictly prohibited.

3.3. CHANGES TO ANALYSIS FROM PROTOCOL

No change to analysis from protocol is planned.

4. PLANNED ANALYSES

The following analyses will be performed for this trial:

- Primary Analysis (after primary endpoint is available)
- Final Analysis (after Database lock, based on all available data)

This document will provide details for Primary Analysis and Final Analysis.

The analyses described in this SAP will be performed by Biostatistics following Sponsor Authorization of this Statistical Analysis Plan, Sponsor Authorization of Analysis Sets and Data Snapshot/Database Lock.

4.1. PRIMARY ANALYSIS

The primary analysis will take place when all primary efficacy endpoint data are available and cleaned (i.e., approximately 4 weeks after the last patient has been randomized). The cut-off date will be the date on which the last patient completes the Week 4 visit and will be the same for all patients. A database snapshot will be taken with regard to this cut-off date; it will include data available in the database up to and including the cut-off date of Week 4 visit and will be used for performing the analysis (please refer to APPENDIX 4). Only cumulative results will be presented, i.e., patient level data will be excluded meaning that N, mean and SD will be displayed instead of usual summary statistics. Indeed, there may be a risk for unblinding when presenting individual data such as minimum or maximum values, quartiles together with the treatment groups. Only a selected team, not involved in any other trial activities, will have access to the unblinded snapshot data and will be required to sign a confidentiality agreement. Efficacy data and all available data for safety and other endpoints will be included up to the Week 4 visit only. To ensure that the data integrity of the continuing trial will not be violated, a charter will be prepared in advance, outlining the procedures to be followed. This document will describe the measures to be implemented by the Sponsor to protect the integrity of the trial until the final database lock. Team members involved in the conduct of the trial as well as the site personnel and patients will remain blinded until the final database lock. A separate clinical trial report (CTR) will not be prepared for this analysis; rather it will be attached to the final CTR.

4.2. FINAL ANALYSIS

A final analysis (including all endpoints) will be performed when all trial data are available, i.e., approximately

Document:	\\ieedc-vnasc01\BIOSdata\Boehringer_Ingelheim\BI_695501\NVA96252\Biostatistics\Documentation\SAP\BI1297.4 SAP FINAL v4.0_22MAY2019.docx		
Author:	Version Number:	Final V4.0	
	Version Date:	22MAY2019	
Template No: CS_TP_BS016	Revision 5	Reference:	CS_WI_BS005
Effective Date:	01Apr2018		

56 weeks after the last patient has been randomized. In this analysis, all analyses performed for the primary analysis will be repeated with the (partially) updated data, in particular with respect to safety and efficacy endpoints collected until Week 56. The results of the final analysis will be summarized in a CTR.

5. ANALYSIS SETS

Agreement and authorization of subjects included/excluded from each analysis set will be conducted prior to the unblinding of the dedicated staff for primary analysis (Week 4), and unblinding for final analysis (Week 56). The analysis sets will be checked at the time of final analysis and may be updated according to data entered in the database at the time of database lock.

5.1. ALL SUBJECTS ENROLLED SET [ENR]

The all subjects enrolled (ENR) set will contain all subjects who provide signed informed consent for this trial.

5.2. ALL SUBJECTS RANDOMIZED SET [RND]

The all subjects randomized (RND) set will contain all subjects in the ENR set who were randomized to trial medication.

For analyses and displays based on RND, subjects will be classified according to randomized treatment.

5.3. FULL ANALYSIS SET [FAS]

The full analysis set (FAS) will contain all randomized patients who received at least 1 dose of trial medication, and have all efficacy measures relevant for the CDAI, measured at baseline and at least once post-baseline (on Week 4).

For analyses and displays based on FAS, subjects will be classified according to randomized treatment.

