7.3 PLANNED ANALYSES

The primary analysis set will be the FAS according to the intention to treat principle. The FAS will consist of all randomized patients who receive at least one dose of trial medication, and have all efficacy measures relevant for the CDAI, measured at baseline and at least once post-baseline.

A PPS of patients who have followed the CTP in all essential criteria will be created for sensitivity analyses. Patients included in the FAS who have important protocol violations relevant for efficacy prior or at Week 4 will be excluded from the PPS. Protocol violations will be assessed on a case-by-case basis. A protocol violation will be considered important if it can be expected to have a distorting influence on the assessment of the primary endpoint. Important protocol violations may include:

- Incorrect trial medication taken until Week 4
- Violation of treatment compliance until Week 4
- Violation of inclusion/exclusion criteria
- Further details on the definition of the different analysis sets will be provided in the TSAP.

All patients treated with at least one (full or partial) dose of either of the trial treatments during any dosing period will be included in the safety evaluation (SAF).

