7.3.1 Primary endpoint analyses

Primary efficacy analysis:

The primary analyses will be performed on the FAS. Patients will be assigned to the treatment they were randomized to receive.

The primary analysis of the observed proportion of patients with a clinical response (CDAI decrease of \geq 70 compared with baseline) at Week 4 will be based on log-linked binomial model. No missing data imputation for primary analysis endpoint need to be taken into account due to FAS definition. However, for pre-specified criteria non-responder imputation (NRI) will be applied (see Section 7.5).

The statistical model can be described as follows:

• (M1) Response to treatment at Week 4 = treatment + prior infliximab exposure + screening SES-CD

This model includes the stratification factor, prior exposure to infliximab, and treatment as fixed, categorical effects and it will be investigated whether the baseline SES-CD will be included as a continuous or as a categorical effect:

- Treatment (BI 695501, EU-approved Humira)
- Prior exposure to infliximab (Yes/No)
- Baseline SES-CD ($<16 \text{ or } \ge 16$)

The relative risk estimate together with its 90% and 95% CI (ratio scale) will be produced.

Further efficacy analyses:

As sensitivity analyses to the primary analysis, the primary endpoint will also be analyzed on the PPS with NRI.

The following explorative hypotheses are not intended to support any biosimilarity claim for BI 695501; however, the framework of non-inferiority testing will be used to compare efficacy of BI 695501 versus EU-approved Humira in a descriptive way.

The following hypotheses will be investigated:

- H_0 : RR of proportion of patients with a clinical response (CDAI decrease of \geq 70 compared with baseline) at Week 4 (BI 695501 versus EU-approved Humira) is less than or equal to 0.76
- H₁: RR of proportion of patients with a clinical response (CDAI decrease of ≥70 compared with baseline) at Week 4 (BI 695501 versus EU-approved Humira) is greater than 0.76

Two-sided 90% CI will be used for the comparison.

The applied margin (0.76 on the ratio scale for CDAI 70) does preserve 39% of the historical effect of adalimumab over placebo (based on a meta-analysis of GAIN and CLASSIC1; see Appendix 10.3 for further details).

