7.5 HANDLING OF MISSING DATA

7.5.1 Efficacy endpoints

No missing data for the primary analysis endpoint are expected for the FAS, because Week 4 is the first post-baseline visit for efficacy assessment and, in case of discontinuation prior to Week 4, the EoT efficacy assessments should be performed. However, all patients who

discontinue treatment, are lost-to-follow-up or have any major protocol deviation related to any therapy that may significantly impact efficacy assessment (Table 4.2.2.1: 1) prior to the primary endpoint assessment will be considered as non-responders. Patients without any available CDAI evaluation at Week 4 will also be considered as non-responders. This is referred to as 'NRI'. Patients assessed as non-responders at Week 4 will be considered non-responders for all subsequent time points (LOCF).

For secondary efficacy endpoints, rules for handling of missing data will be specified in the TSAP, if necessary.

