15. EFFICACY OUTCOMES

15.1. PRIMARY EFFICACY

15.1.1. PRIMARY EFFICACY VARIABLE & DERIVATION

The primary efficacy endpoint is:

- The proportion of patients in each treatment group with a clinical response (CDAI decrease of ≥ 70 compared with baseline) at Week 4

CDAI decrease at Week 4 is assessed as the decrease relative to baseline measurement:

- Decrease = CDAI at Baseline - CDAI at Week 4

In case of baseline value equal to 0 or missing post-baseline value recorded, then the change is set to 0 for the corresponding visit (no decrease).

Subjects with a decrease greater or equal to 70 are responders. Other subjects are considered as non-responders.

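### The SAP's Week 4 non-responder rule omits the protocol's therapy-deviation trigger, and its FAS wording, read literally, drops some early discontinuers

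*SAP*

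**What the plan says.** **Protocol.** Section 7.3 states: "The primary analysis set will be the FAS according to the intention to treat principle". It defines the FAS as randomised, dosed patients who "have all efficacy measures relevant for the CDAI, measured at baseline and at least once post-baseline", and names no visit. Section 7.3.1 adds: "No missing data imputation for primary analysis endpoint need to be taken into account due to FAS definition". It then says that "for pre-specified criteria non-responder imputation (NRI) will be applied" and points to Section 7.5. Section 7.5.1 sets out this non-responder imputation (NRI). It covers patients who, before the primary assessment, "discontinue treatment, are lost-to-follow-up or have any major protocol deviation related to any therapy that may significantly impact efficacy assessment" (with a reference to Table 4.2.2.1: 1). It goes on: "Patients without any available CDAI evaluation at Week 4 will also be considered as non-responders".

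**SAP.** Section 3.3 declares no change from the protocol's analysis. Section 5.3 repeats the FAS definition but ends it differently: patients must "have all efficacy measures relevant for the CDAI, measured at baseline and at least once post-baseline (on Week 4". Section 15.1.1 covers a missing value in these words: "missing post-baseline value recorded, then the change is set to 0 for the corresponding visit (no decrease". Section 15.1.2 lists two NRI triggers for Week 4, stopping treatment and loss to follow-up. It also expects an End of Treatment (EoT) efficacy assessment from anyone who stops earlier.

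**The concern.** The main result is one risk ratio (RR) with its confidence interval. It depends on who is in the FAS and who in it counts as a responder, and the SAP is the text that gets programmed. Two of its provisions differ from the protocol without being declared: the missing therapy trigger changes the numerator, and the parenthesis in 5.3 can change the denominator. A third problem lies inside the protocol: entry to a set described as intention to treat depends on an assessment made after randomisation.

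If the affected counts differ between arms, the RR moves in a direction that cannot be known in advance. If the counts and the underlying response are equal, the RR stays put, but both reported response rates are too high relative to the protocol's rule.

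**Working it through.** **The triggers side by side**

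| Week 4 non-responder because of | Protocol 7.5.1 | SAP |
|---|---|---|
| Treatment stopped before Week 4 | yes | yes, 15.1.2 |
| Lost to follow-up before Week 4 | yes | yes, 15.1.2 |
| Major deviation on a therapy affecting efficacy | yes | absent for Week 4 |
| No Week 4 CDAI | yes | equivalent in 15.1.1 (change set to 0) |

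The SAP does know the third trigger: it stands in the footnote to Table 1 in 15.2.2, for Week 24. There it acts only when CDAI cannot be computed, because both columns of the table use the observed value otherwise. Step 2 of 15.2.2 then refers back to 15.1.2, which lacks it.

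**What happens to three kinds of treated patient**

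| Patient | Protocol | SAP as worded |
|---|---|---|
| A. Therapy deviation before Week 4, stays on treatment, CDAI falls by 70 or more | in FAS, non-responder | in FAS, responder |
| B. Stops before Week 4, only complete post-baseline CDAI is at EoT | in FAS (7.3), non-responder (7.5.1) | outside FAS if 5.3 is read literally |
| C. No complete post-baseline CDAI | non-responder by 7.5.1, outside FAS by 7.3 | outside FAS |

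For B, SAP 6.3 keeps early-termination data at the EoT visit in by-visit summaries and 6.4 does no re-windowing, so nothing turns an EoT value into a Week 4 value.

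**Size.** Inputs from Protocol 7.7: 65 per arm and 80% response, hence 0.80 × 65 = 52 responders. From Protocol 7.3.1: a two-sided 90% CI and a descriptive margin of 0.76. The documents give no dropout or deviation rate, so every count of affected patients below is an assumption.

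The plan's own precision figure reproduces: 1.645 × √(2 × 0.8 × 0.2 / 65) = 0.115. That is a half-width for a risk difference, which Table 7.7: 1 places around an RR of 1. For the RR I use the unadjusted log-scale form:

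SE = √(1/x₁ − 1/n₁ + 1/x₂ − 1/n₂), CI = RR × exp(±1.645 × SE).

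Reference, 52/65 in both arms: SE = √(2 × (1/52 − 1/65)) = 0.0877, so RR 1.00 (0.866–1.155).

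*Patient A* (deviating responders, BI 695501 vs Humira). The SAP gives the reference result when nobody is reclassified. The protocol gives:

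| Count | Rates | RR (90% CI) |
|---|---|---|
| 1 vs 0 | 51/65 vs 52/65 | 0.981 (0.846–1.137) |
| 2 vs 0 | 50/65 vs 52/65 | 0.962 (0.827–1.119) |
| 3 vs 0 | 49/65 vs 52/65 | 0.942 (0.807–1.100) |
| 0 vs 3 | 52/65 vs 49/65 | 1.061 (0.909–1.239) |
| 2 vs 2 | 50/65 in both | 1.00, with 76.9% reported instead of 80% |

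*Patient B* (non-responders removed by the literal SAP wording). The protocol gives the reference result. The SAP gives:

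| Count | Rates | RR (90% CI) |
|---|---|---|
| 1 vs 0 | 52/64 vs 52/65 | 1.016 (0.881–1.171) |
| 2 vs 0 | 52/63 vs 52/65 | 1.032 (0.897–1.186) |
| 0 vs 2 | 52/65 vs 52/63 | 0.969 (0.843–1.114) |
| 2 vs 2 | 52/63 in both | 1.00, with 82.5% reported instead of 80% |

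*Distance to 0.76.* Suppose instead 80% response among those who remain, with early discontinuers only in the BI 695501 arm. With 6 of them, NRI gives RR 0.908 with lower limit 0.772. With 8 (0.8 × 57 = 45.6 of 65), it gives 0.877 with lower limit 0.742. Exclusion leaves RR 1.00 in both cases.

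**The case against.** **The parenthesis may be only a gloss.** SAP 15.1.2 names Week 4 as the first efficacy visit after baseline, relies on EoT assessments for early discontinuers and sets them to non-responder within the FAS. That rule makes full sense only if they are in the FAS. This stands: a reader might infer that the SAP deliberately redefined the primary population, and the documents do not support that. What remains is wording with two readings in the place that fixes the primary denominator.

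**The protocol is less contradictory than it looks.** A reader might infer from 7.3.1 that no imputation applies at all. It does not say so: it keeps NRI in the next sentence. For patient B, 7.3 and 7.5.1 fit together. The tension is confined to patient C, and since both documents exclude C, it is not a SAP departure.

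**The per-protocol set might catch the therapy deviations.** It partly can. SAP 5.4 names EC25 (restricted drugs continued from entry), EC8 and EC14 (certain earlier drugs), and its list is open. So it would be wrong to say that the per-protocol set ignores restricted therapy. But a restricted drug started or changed after randomisation is not named. The sentence in SAP 9.1 that its violations are not those excluding patients from the per-protocol sets is unclear, because 9.1 also lists wrong treatment and unmet entry criteria, which 5.4 treats as possible grounds for exclusion. In any case this set serves a sensitivity analysis and does not restore NRI in the FAS.

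**The discontinuation rule catches some deviators.** Protocol 3.3.4.1 provides for stopping treatment when an interfering drug is needed, and such patients are non-responders under both documents. Those who are not discontinued are missed.

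**Conclusion.** The main point holds on the text alone: the SAP's Week 4 rule lacks a trigger that the protocol applies to the primary endpoint, and SAP 3.3 says that nothing changed. The FAS parenthesis is a departure on its literal reading and needs correcting either way. The point on patient C is a narrow inconsistency within the protocol.

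The effect is modest. With one to three affected patients in one arm, the RR shifts by about 0.02 to 0.06. A reader might infer that a similarity conclusion is at risk. The documents do not support that: Protocol 7.2 sets no confirmatory hypothesis and 7.3.1 disclaims any biosimilarity claim. In the two tables every lower limit stays at or above 0.807, and it took 8 against 0 early discontinuers to pass 0.76. The stake is the accuracy of the estimate and of the reported response rates. The sizes rest on assumed counts, the protocol's 80% response and an RR unadjusted for the stratification factors. The textual discrepancy rests on none of these.

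**What to change.** - **SAP 15.1.2:** add the therapy-deviation trigger of protocol 7.5.1, applied before the Week 4 assessment, with affected patients identified before unblinding.
- **SAP 5.3:** delete the Week 4 parenthesis so that the FAS matches protocol 7.3.
- **SAP 3.3:** if either departure is intended, declare it here.
- **Sensitivity analysis:** keep the protocol FAS as the primary set, and add an analysis of all randomised, treated patients with a baseline CDAI in which those without a Week 4 CDAI are non-responders. Making that wider set primary in the SAP would itself depart from protocol 7.3.
- **Protocol:** reconcile 7.3 with 7.5.1 at the next amendment, with the approvals in Protocol 8.1.

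The SAP changes are wording edits plus one extra analysis. The price is slightly lower response rates and slightly wider intervals. Assuming 80% response among those remaining, 2 patients lost per arm and counted as non-responders give 50.4/65 = 77.5% and a 90% CI of 0.856–1.168, against 80% and 0.864–1.158 if excluded. With 6 per arm the figures are 47.2/65 = 72.6% and 0.838–1.194, against 80% and 0.859–1.163.

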5.4. PER PROTOCOL ANALYSIS SET [PPS]

The per-protocol analysis set (PPS) will contain all subjects in the FAS who did not experience any important protocol violations relevant for efficacy. Important protocol violations will be reviewed and approved prior to the Data Snapshot/Database Lock. However, additional unexpected protocol deviations may be added afterwards. Two Per Protocol Analysis Sets will be analyzed. One PPS for the Primary Analysis based on the week 4 data

Document:	\\ieedc-vnasc01\BIOSdata\Boehringer_Ingelheim\BI_695501\NVA96252\Biostatistics\Documentation\SAP\BI1297.4 SAP FINAL v4.0_22MAY2019.docx		
Author:	Version Number:	Final V4.0	
	Version Date:	22MAY2019	
Template No:	CS_TP_BS016	Revision 5	Reference: CS_WI_BS005
Effective Date:	01Apr2018		

(primary efficacy endpoint) (PPS) and one for the Final Analysis based on the week 24 data (secondary efficacy endpoint) (PPS2).

The important protocol violations may include but are not limited to:

- Incorrect trial medication taken. Kit numbers which were actually used for the preparation of the trial drug will be recorded on the eCRF. Defined as, on the patient level, at least one kit number used before Week 4 – for Primary Analysis PPS – and before Week 24 – for Final Analysis PPS – does not correspond to the initial randomized treatment group.
- Important violation of treatment compliance prior to Week 4 – for Primary Analysis PPS – and prior to Week 24 – for Final Analysis PPS: medical team will review subjects with treatment compliance outside 80% and 120% (refer to section 14.1) and decide if the violation is severe.
- Important violation of inclusion/exclusion criteria
 - IC1
 - IC2
 - EC1
 - EC7
 - EC8
 - EC9
 - EC10
 - EC14
 - EC21
 - EC25
 - EC27
 - EC28

Document: \\ieedc-vnasc01\BIOSdata\Boehringer_Ingelheim\BI_695501\NVA96252\Biostatistics\Documentation\SAP\BI1297.4 SAP FINAL v4.0_22MAY2019.docx

Author: Version Number: Final V4.0
Version Date: 22MAY2019

Template No: CS_TP_BS016 Revision 5
Effective Date: 01Apr2018

Reference: CS_WI_BS005

5.5. SAFETY ANALYSIS SET [SAF]

The safety analysis set (SAF) will contain all subjects in the RND set who receive at least one dose (full or partial) of trial medication.

If there is any doubt whether a subject was treated or not, they will be assumed treated for the purposes of analysis.

For analyses and displays based on SAF:

- In case the subject was fully incorrectly treated, the subject will be classified according to treatment received
- In case the subject was partially incorrectly treated, the subject will be classified according to treatment

6. GENERAL CONSIDERATIONS

6.1. REFERENCE START DATE AND STUDY DAY

Study Day will be calculated from the reference start date, and will be used to show start/stop day of assessments and events. It will appear in every listing where an assessment date or event date appears.

Document:	\\ieedc-vnasc01\BIOSdata\Boehringer_Ingelheim\BI_695501\NVA96252\Biostatistics\Documentation\SAP\BI1297.4 SAP FINAL v4.0_22MAY2019.docx		
Author:	Version Number:	Final V4.0	
	Version Date:	22MAY2019	
Template No:	CS_TP_BS016	Revision	5
Effective Date:	01Apr2018		Reference: CS_WI_BS005

Reference start date is defined as the day of the first dose of study medication, (Day 1 is the day of the first dose of trial medication), or for subjects randomized but not treated it is the day of randomization.

- If the date of the event is on or after the reference date then:

Study Day = (date of event – reference date) + 1.

- If the date of the event is prior to the reference date then:

Study Day = (date of event – reference date).

In the situation where the event date is partial or missing, Study Day, and any corresponding durations will appear partial or missing in the listings.

6.2. BASELINE

Unless otherwise specified, baseline is defined as the last non-missing measurement taken prior to reference start date (including unscheduled assessments). In the case where the last non-missing measurement and the first dose of trial medication date coincide, that measurement will be considered as baseline.

6.3. RETESTS, UNSCHEDULED VISITS AND EARLY TERMINATION DATA

In general, for by-visit summaries, data recorded at the nominal visit will be presented. In the case of a retest, an unscheduled assessment will be created. For laboratory assessments as described in APPENDIX 5, the latest available measurement within acceptable timeframe after the planned assessment will be used for by-visit summaries. Unless assigned to a planned visit number, unscheduled measurements will not be included in by-visit summaries.

Treatment early termination data will be included in End-of-Treatment visit in by-visit table summaries and by-visit graphs, according to the protocol.

Listings will include scheduled, unscheduled, and retest data as collected in the eCRF database.

